In pre-operative and post-operative samples.1 the complete blood count will be performed and Tn-hs, NT-proBNP and LDH will be dosed RNA analysis will be divided into two phases: in the discovery phase, the analysis of the transcriptome by RNA sequencing. The aim is to identify a potential ACS_signature in blood mononucleate cells (PBMCs) of a subset of patients who eventually of the follow up of the discovery phase, show ventricular dysfunction (n= 40) or function conserved ventricular (n= 40). An equal number of STEMI and NSTEMI patients will be analysed.

In the validation phase, the ACS_signature will be measured with independent technique (qPCR) in all patients enrolled in the study, to obtain a Validated ACS-Signature.

Study procedures

They will be taken at each time-point: 1) 3 ml of whole blood in a tube containing stabilizers RNA (type PAX-gene or Tempus), 2) 4 ml in a tube containing EDTA from which the plasma that will be frozen at -80,5° C pending the extraction of RNA, and 3) 4 ml in a tube containing EDTA from which PBMCs will be isolated. The withdrawals in point 2 and 3 must be processed within two hours of the withdrawal, while the withdrawal in tube with RNA stabilizer can be stored at room temperature for up to 3 days, at +4 killed C for 7 days and at -20 killed C/-80 killed C indefinitely without altering the integrity of nucleic acids. Plasma and whole blood RNA will be extracted by silica columns, while RNA from PBMCs will be extracted by Trizol. The integrity of the extracted RNA will be evaluated by running on capillary gel type Bioanalyzer.

On RNA extracted from PBMCs derived from pre-operative sampling in the discovery group, it will be analysis of the entire transcriptome by RNA sequencing (platform Illumina), in order to identify a potential ACS_signature consisting of transcripts differentially expressed in the two groups of patients: those with left ventricular dysfunction and those without ventricular dysfunction.

In the validation phase, the potential ACS_signature will then be validated by qPCR in all STEMI and NSTEMI patients enrolled in the study, including those who will submit a degree intermediate ventricular dysfunction (LVEF 45-49%). They will also be analysed separately two subgroups of patients diagnosed with STEMI and NSTEMI.

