RNA that will pass validation (Validated ACS_Signature), will be further tested also in the AU control group and all other timepoints, to assess the time trend potential biomarkers. In addition, the expression of the Validated ACS-Signature will be evaluated in the plasma and whole blood, to assess biodistribution and translational potential. Patient recruitment, withdrawals, patient data collection and all clinical procedures requests will be made by the Clinical, Interventional and Intensive Care Cardiology Unit Coronary Surgery (UTIC) of the IRCCS Policlinico San Donato. The collection and conservation of blood and pre-analytic treatment will be carried out at the BioCor Biobank of the IRCCSPoliclinico San Donato, while RNA measurements will be carried out in the Laboratory of Molecular Cardiology of IRCCS Policlinico San Donato. The study of modulated transcripts by RNA Sequencing with library preparation, sequencing and analysis bioinformatics will be carried out at the Center for Translational Genomics and bioinformatics, of the San Raffaele Hospital.

Sample size

Based on literature [4, 5] it is expected that about 40% of STEMI patients and 30% of STEMI patients NSTEMI patients, after a first episode of myocardial infarction, experience dysfunction of the left ventricle.

Based on these data, we expect recruiting in 18 months 278 patients with ACS performing PCI, 100 will experience ventricular dysfunction (Table 1).

Table 1. Patient recruitment and follow up				
Study phase	Total number of patients		Dysfunction LV expected	
	STEMI	NSTEMI	STEMI	NSTEMI
DISCOVERY	49	75	20	22
VALIDATION	61	93	31	28
TOTAL STEMI + NSTEMI	110	168	50	50

The number of patients to be recruited will be 378, of which 110 STEMI, 168 NSTEMI and 100 AU, as control. By preventing 100 events in total, respectively 50 per group, you can enter about 6/7 variables for each model of multivariate logistic regression (STEMI NSTEMI). Experimental RNA measurement activities shall follow the distribution shown in Table 2.

Table 2. Experimental activity				
	DISCOVERY		VALIDATION	
	STEMI	NSTEMI	STEMI	NSTEMI
LV DYSFUNCTION	20	20	50	50
NO LV DYSFUNCTION	20	20	60	118
TOTAL	40	40	110	168

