For discovery activities using RNA-sequencing, based on literature data [16], we assume a sample size of 40 patients (20 per group) to evaluate the 40 transcripts that differentiate patients with ventricular dysfunction and not ventricular dysfunction, out of a total of 17,500 tests, considering a power of 94.0 %, a value of FDR equal to 0.02. For the activities of validation using qPCR, 95% power is obtained by analyzing 50 samples per group evaluating differences between the averages of 2,2 times, with $\alpha=0,01$ and $\sigma=1,4$.

Statistical methods

The characteristics of patients will be presented with the average, median, standard deviation and range interquartile for continuous and frequency variables and % for nominal and categorical variables. The Shapiro-Wilks will be used to check if distributions are Gaussian. For distributions normal, statistical analysis will be carried out with parametric tests while for non-normal distributions a non-parametric statistical analysis will be carried out. Logistic regression models will be used to assess the association between gene characteristics and clinical outcome. In particular, the power discriminatory (c statistics) will be expressed in terms of area under the curve in a Receiver Operating Characteristics (ROC) analysis. Different cut-off levels will be explored for each of which sensitivity, specificity, negative predictive power and positive predictive power will be evaluated. The added prognostic value of ACS_signature in relation to variables will also be assessed traditional clinics including NTproBNP, Tn-hs and CK-MB using the prediction curve.

Ethical aspects

The study will be conducted according to GCP, local laws and rules of the World Medical Association Declaration of Helsinki.

Publication policy

The data collected are the property of IRCCS Policlinico San Donato and will be the subject of publication.

Bibliography

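### If a best cut-off is singled out, or model weights are fitted, in the same STEMI and NSTEMI patients, the reported accuracy is too high; the protocol states no correction

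*Protocol*

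**What the plan says.** Statistical methods (Protocol) uses logistic regression to relate gene characteristics to outcome. It adds that "the power discriminatory (c statistics) will be expressed in terms of area under the curve", and then: "Different cut-off levels will be explored for each of which sensitivity, specificity, negative predictive power and positive predictive power will be evaluated". It gives no rule for choosing among the levels and does not say that one will be chosen.

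Study procedures (Protocol) says that "the potential ACS_signature will then be validated by qPCR in all STEMI and NSTEMI patients enrolled in the study", and continues: "They will also be analysed separately two subgroups of patients diagnosed with STEMI and NSTEMI".

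Sample size (Protocol) gives the numbers: "The number of patients to be recruited will be 378, of which 110 STEMI, 168 NSTEMI and 100 AU, as control". It expects 100 cases of ventricular dysfunction, 50 in each infarct type, and on that basis allows "6/7 variables for each model of multivariate logistic regression". Table 2 sets the qPCR validation at 50 with and 60 without dysfunction in STEMI, and 50 and 118 in NSTEMI. These are the full STEMI and NSTEMI totals of Table 1, so discovery-phase patients are included.

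No held-back set, resampling or optimism correction is mentioned.

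**The concern.** A cut-off that looks best in a sample does so partly by chance. Scoring it in that sample counts the chance as performance. The same holds for logistic weights: the AUC of a fitted model, read in the patients who produced the weights, exceeds 0.50 on average even if no variable carries information. Both effects grow as cases become fewer, so they are larger in the separate STEMI and NSTEMI analyses than in the pooled one.

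Because validation takes in everyone with STEMI or NSTEMI, no patients of those types remain in whom a cut-off or model could be tested afresh. Sensitivity, specificity and predictive values are the figures by which readers would judge a prognostic signature. If they carry this optimism, the next cohort will not reproduce them.

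**Working it through.** **Inputs.** From Table 2: cases/non-cases of 50/60 (STEMI), 50/118 (NSTEMI) and 100/178 (pooled). From Sample size: 6 to 7 variables per model, and for qPCR a 2.2-fold difference, SD 1.4, alpha 0.01, 50 per group and 95% power. Two assumptions are mine: the SD is in log2 units, and the cut-off singled out is the one with the largest J.

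**Check of the protocol's own figure.** The standardised difference is log2(2.2)/1.4 = 1.1375/1.4 = 0.8125. With 50 per group the test statistic is centred at 0.8125 × √(50/2) = 4.06. One-sided power at alpha 0.01 is Φ(4.06 - 2.326) = 95.9%; two-sided it is Φ(4.06 - 2.576) = 93.1%. The stated 95% is reproduced on the log2 reading, best as a one-sided test. Reading the difference as ln(2.2) gives 59% to 69%, which does not match.

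**Definitions.** J = sensitivity + specificity - 1. Apparent J is the maximum over cut-offs c of TP(c)/cases - FP(c)/non-cases, all in one sample. True J is the population value at the cut-off so chosen.

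**1. Worthless single marker, direction fixed** (10,000 simulated data sets per setting; true J = 0):

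| | STEMI | NSTEMI | Pooled |
|---|---|---|---|
| One cut-off fixed beforehand | 0.00 | 0.00 | 0.00 |
| Best of 3 cut-offs | 0.053 | 0.046 | 0.035 |
| Best of 9 cut-offs | 0.081 | 0.072 | 0.053 |
| Best of all cut-offs | 0.111 | 0.101 | 0.075 |

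In STEMI, the best of all cut-offs gives a mean PPV of 0.55 against an event rate of 50/110 = 0.455, and a mean NPV of 0.64 against 60/110 = 0.545. If the direction of the marker is also taken from the data, J rises to 0.16, 0.14 and 0.105.

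**2. Marker with the protocol's own effect** (5,000 data sets per setting). The true AUC is Φ(0.8125/√2) = 0.717 and the best attainable J is 2Φ(0.8125/2) - 1 = 0.315.

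| | STEMI | NSTEMI | Pooled |
|---|---|---|---|
| Apparent J | 0.383 | 0.375 | 0.356 |
| True J at the chosen cut-off | 0.296 | 0.298 | 0.303 |
| Overstatement | 0.087 | 0.077 | 0.053 |

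In STEMI that is 0.087/0.296, or about 29% in relative terms; pooled it is 0.053/0.303, about 17%.

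**3. Six worthless variables fitted by logistic regression** and scored in the same patients (1,500 data sets per setting). Apparent AUC is 0.63 in STEMI and 0.61 in NSTEMI, against a true 0.50. Apparent J at the best cut-off is 0.26 and 0.23, against a true 0; these values combine overfitting of the weights with the cut-off search.

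**The case against.** **Selection is an inference.** A reader might conclude that the protocol picks a best cut-off and reports its accuracy. The text does not say so. It describes evaluating accuracy at each level explored, and showing all levels of a fixed score without preference overstates none of them. This objection stands, and it makes the point conditional. Singling out a level is nevertheless the natural next step for a predictive signature, and nothing in the protocol prevents it or corrects for it.

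**The size can be overdrawn.** A reader might infer that accuracy is nearly doubled. That needs a weak marker: at a true AUC of 0.60, STEMI shows J of 0.226 against a true 0.125. The protocol contains no such AUC. Its own effect size gives the smaller overstatement above, and a coarse search of three cut-offs gives roughly half the full-search figure for a worthless marker.

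**The AUC is not always affected.** The AUC of a score fixed beforehand does not depend on any cut-off and is not biased by the search. The AUC part of the point applies only where weights are fitted and scored in the same patients.

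**A statistical analysis plan may deal with this.** It may, and the lack of resampling detail would not by itself be a finding. What the protocol does fix is an open cut-off search, fitted multivariable models, and validation in every STEMI and NSTEMI patient. Together these leave optimism correction as the only safeguard within those patients.

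**Conclusion.** The point holds in conditional form. If a best cut-off is singled out in the validation data, J is overstated by about 0.075 to 0.11 for a worthless marker and by about 0.05 to 0.09 at the protocol's own effect size. If weights for six uninformative variables are fitted and scored in the same patients, an AUC of 0.61 to 0.63 is to be expected by chance in the two infarct types.

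These sizes rest on a normally distributed marker, a best-Youden search over all cut-offs, the log2 reading of the SD, and the stated 50 events per type. The optimism is modest for one pooled marker and more material in the separate STEMI and NSTEMI analyses. The documents do not support saying that the accuracy figures will be biased whatever is reported. The 95% power figure is not affected. This is a cheap improvement worth making, not a fault that invalidates the design.

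**What to change.** In Statistical methods, state that the AUC, and the sensitivity, specificity, PPV and NPV at any cut-off singled out, will be reported with bootstrap optimism correction and confidence intervals. Each resample must repeat both the model fitting and the cut-off search. State that all other cut-offs are exploratory. This needs no new patients or samples, only wording and a short resampling program; the reported accuracy will be less favourable. It does not undo the earlier selection of transcripts by RNA sequencing in patients who are also in the validation set.

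Alternatively, lock the weights and the cut-off in the discovery-phase patients and report accuracy only in the validation-phase patients of Table 1: 61 STEMI with 31 expected events and 93 NSTEMI with 28. Scoring the locked rule in all 278 would not do, because that set includes the patients who produced it.

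The price of the alternative is precision. At a sensitivity of 0.65, taken for illustration, the approximate 95% half-width is 1.96 × √(0.65 × 0.35/n). That is 0.13 with 50 events, 0.17 with 31 and 0.18 with 28. The 31 is as printed in Table 1; the protocol's 40% rate would give 0.40 × 61 = 24.4 STEMI events and a half-width of 0.19.

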3.2. EXP ACTIVITY VALIDATION: VALIDATED ACS_SIGNATURE																																									
3.3. CODE BROKEN, CORRELATIONS AND STAT ANALYSIS																																									

Assessments	Pre-procedure	Post-procedure (12-24 h)	6 months	12 months
Medical History*	X		X	X
Recruitment criteria	X			
Blood draw ACS_SIGNATURE	X	X	X	X
Blood count*	X	X	X	X
Blood draw Tn-hs e CK-MB*	X	X		
ECG*	X	X	X	X
Echocardiography *	X	X	X	X
Angiography *	X			
Endpoints			X	X

* routine clinical evaluations

Patients will be enrolled after diagnosis of ACS and before coronary surgery and will be treated according to the guidelines provided for the treatment of acute coronary syndrome and for post-PCI. Unless special contraindications, all patients will receive optimal medical therapy that includes:

- Dual therapy for 12 months
- Statins
- beta-blockers,
- ACE inhibitors,
- Mineralocorticoid receptor antagonists.

Follow-up visits including echocardiographic examination will be performed at 6 and 12 months from myocardial revascularization procedure. The evaluation of the FEVS will be carried out by 3D echocardiography that, as has been documented, shows a proven concordance with the MRI [15]. This method has also shown high reproducibility, with low intra- and inter-operator variability, and increased diagnostic accuracy. During the echocardiographic examination, in addition to FEVS data, other function indices will be evaluated systolic left ventricle such as, for example, telesistolic volumes, telediastolic, parameters tissue Doppler derivatives and myocardial strain indices (global Longitudinal strain).

The study will also need to take samples that will be made with the following scheme: 1) pre operative, before PCI, 2) post-operative 1 taken at 12 - 24h from PCI, 3) post-operative2 -6 months after PCI and 4) post-operative3-12 months after PCI.

Pre-operative withdrawal will be performed in the recovery room of the hemodynamics room after diagnosis of ACS. The post-operative withdrawal.1 will be performed at the Department of Cardiology 12/24 hours after the procedure. Post-operative.2 and post-operative.3 withdrawals will be performed outpatient during the planned echocardiographic checks (6 and 12 months respectively).

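### Pre-PCI LVEF is measured but given no stated role in the validation and added-value analyses, so a correlate of entry LVEF could be read as a predictor of evolution

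*Protocol*

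**What the plan says.** **Aim.** Objective of the project seeks circulating biomarkers that predict ventricular dysfunction, defined as ejection fraction below 45%. Patients are to be distinguished by whether they evolve towards it. Study design places that development at 12 months.

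**Entry.** Exclusion Criteria items 7 and 10 remove patients with LVEF below 30% before PCI, and those with known previous cardiomyopathy and LVEF below 40%. Other patients may enter at 30-44%.

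**Measurement.** In the assessments table the row "Echocardiography" is marked before the procedure, after it, and at 6 and 12 months. The signature blood is marked at the same times.

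**Discovery.** The groups are formed by function at the end of follow-up. On STEMI and NSTEMI the text says "An equal number of STEMI and NSTEMI patients will be analysed". The contrast is made "On RNA extracted from PBMCs derived from pre-operative sampling in the discovery group".

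**Validation and added value.** Statistical methods says "Logistic regression models will be used to assess the association between gene characteristics and clinical outcome" and names no covariate. Added prognostic value is assessed against "traditional clinics including NTproBNP, Tn-hs and CK-MB using the prediction curve", without naming the outcome. Sample size states that "you can enter about 6/7 variables for each model of multivariate logistic regression", on 50 events in each of the STEMI and NSTEMI models.

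**The concern.** Entry LVEF is the baseline value of the outcome variable, and it is measured at the same time as the blood sample. The two LVEF values will be correlated, so any transcript that tracks entry LVEF will also be associated with LVEF below 45% at 12 months, even if it says nothing about change.

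Such a transcript could pass validation. It could also appear to add to NT-proBNP, Tn-hs and CK-MB, because those three capture entry LVEF only in part. Clinically it would add little to an echocardiogram already done. At stake is the meaning of a positive result. No figure in the Protocol is wrong on this point.

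**Working it through.** **1. The plan's own validation figure.** Inputs from Sample size: 50 per group, 2.2-fold difference, alpha 0.01, sigma 1.4, power 95%. On the log2 scale the difference is log2(2.2) = 1.1375, or 1.1375/1.4 = 0.81 SD. The standard error is 1.4 × √(2/50) = 0.28, so the ratio is 1.1375/0.28 = 4.06.
- One-sided: Φ(4.06 − 2.33) = 95.9%.
- Two-sided: Φ(4.06 − 2.58) = 93.1%.

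The 95% is reproduced to within 2 points. It refers to an unadjusted two-group difference, in which entry LVEF has no part.

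**2. Validation with and without entry LVEF.** The Protocol gives no distribution of entry LVEF, so every input here except the patient and event numbers is an assumption:
- entry LVEF mean 50, SD 9, or mean 55, SD 7, truncated at 30;
- slope of 12-month on entry LVEF 0.5 or 0.7, residual SD 7 or 9;
- one transcript correlated 0.2 or 0.4 with entry LVEF and with nothing else;
- three clinical markers, each correlated 0.4 with entry LVEF;
- event share 50/110 (STEMI) or 50/168 (NSTEMI).

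This gives 32 settings with 1500 replicates each. The transcript is tested by a Wald test at 0.01 in a logistic model.

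| Assumed entry LVEF | Cases already <45% at entry | Three markers, STEMI | Three markers, NSTEMI |
|---|---|---|---|
| mean 50, SD 9 | 41-58% | 1.6-11% | 2.4-18% |
| mean 55, SD 7 | 12-19% | 1.3-8.6% | 1.8-13% |

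With entry LVEF added, the rejection rate is 0.3-1.4% in all 32 settings, close to the nominal 1%. With entry restricted to LVEF ≥45% and no LVEF covariate it is 0.7-7.5%, so restriction alone does not always remove the effect.

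**3. Dependence on the inputs.** A second set of assumptions pools 278 patients, with entry mean 48, SD 9, entry-to-follow-up correlation 0.4-0.8, transcript correlation 0.3-0.7 and no other markers in the model. Rejection at p<0.01 is then 8-100%, with an AUC of 0.54-0.75. With entry LVEF added it is about 0.3-2%. The uncorrected size depends on what is assumed; the effect of adding the covariate hardly does.

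**4. The discovery filter.** From Sample size: 40 transcripts among 17,500 tests, "considering a power of 94.0 %, a value of FDR equal to 0.02". An approximate raw threshold is 0.02 × 40/17,500 = 4.57 × 10⁻⁵. Under the 50/9 inputs, the LVEF-only transcript differs between groups by 0.14-0.44 SD. By the noncentral t distribution it passes with probability:
- 0.012-0.23% at 20 v 20, or 0.06-1.2 of an assumed 500 such transcripts;
- 0.025-1.35% at 40 v 40, or 0.1-6.8 of 500.

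The plan expects 40 transcripts, so few entries on the list would be of this kind under these inputs. The two stages were not simulated jointly. Table 2 puts all 110 + 168 = 278 patients in validation, so the discovery patients are used again.

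**5. Room in the models.** The Protocol's rule implies 50/7 = 7.1 to 50/6 = 8.3 events per variable. Signature score, entry LVEF and three markers make 5 terms, within 6/7. At the Protocol's own 40% rate for STEMI, 0.40 × 110 = 44 events, which support 44/8.3 = 5.3 to 44/7.1 = 6.2 variables. Five still fit.

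**The case against.** - **Covariates are commonly left to the SAP.** The SAP is not shown, the list of clinical variables is open, and 6/7 places exceed the three markers named. This has force: a reader might infer that entry LVEF is ruled out, and the text does not say so. What stands is that the Protocol itself names comparators and omits the baseline value of its own outcome. An open list commits nobody to the comparator that the result most needs.
- **The data exist.** A reader might infer that the study cannot tell the two kinds of marker apart. That is too strong, because the pre-procedure echocardiogram is taken in the same patients. The limit lies in the analysis as written.
- **The added-value sentence names no outcome.** The only objective that mentions value beyond usual clinical measures is the secondary one, on adverse events. This is correct, so the point about LVEF below 45% rests mainly on the validation models. For added value it applies to the extent that the analysis concerns that outcome.
- **The simulated test is not one the Protocol states.** Alpha 0.01 belongs to the qPCR comparison of means, and no text puts the three markers in the validation model. The LVEF-only effect of 0.14-0.44 SD is also well below the 0.81 SD for which validation is sized. The simulation is therefore only an illustration.
- **The entry limit.** A reader might blame admission at 30-44%, or call the outcome invalid. Neither follows. The two LVEF values are correlated whatever the limit, and any LVEF below 45% at 12 months is a coherent outcome.

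**Conclusion.** The point holds as a gap in the stated analysis that should be closed. Run with the named comparators only, a positive validation or added-value result would leave open whether the signature predicts evolution or reflects LVEF already known at entry.

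Its size cannot be derived from the documents. In the illustration with the three markers, the inflation runs from negligible (1.3% against a nominal 1%) to moderate (18%), and discovery would remove most such transcripts first. The documents do not support the inference that a validated signature would consist mainly of LVEF correlates. The interpretive gap does not depend on the size. If a SAP already names entry LVEF in these models, the point is closed.

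**What to change.** In Statistical methods:
- Enter pre-PCI LVEF as a continuous covariate in the STEMI and NSTEMI validation logistic models for LVEF below 45% at 12 months.
- Name pre-PCI LVEF with NT-proBNP, Tn-hs and CK-MB in the reference model for added value.

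**Cost.** This changes analysis wording only, since the echocardiogram is already scheduled. It uses one of the 6/7 variables per model: with the three markers, 2-3 places remain for transcripts instead of 3-4.

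**Optional clarifications.** State whether the outcome is any or new LVEF below 45%. Report patients with entry LVEF ≥45% as a sensitivity analysis with its event count. Under the assumed distributions it keeps about 26-44 of 50 STEMI events and 21-43 of 50 NSTEMI events, so it supports only about 2-6 variables.

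Eligibility and the discovery analysis need not change. Adjusting the discovery contrast could cost power: if cases and controls differ by 0.7-1.3 SD in entry LVEF, 94% at 20 v 20 would fall to about 89-74%.
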